Fasting plasma glucose & serum insulin (f)			Day 8 preAM: 0 ($\leq 15m$)		X		
Clinical chemistry, coagulation, hematology, urinalysis; (f)					X		X
Urine albumin & creatinine (g)					first void		X
AE Evaluations	X	X	X	X	X	X	X
Prior & concomitant medications	X	X	X	X	X	X	X

Study Period→		Clinic Period				Follow-up Period	
Visit Days →	Study Procedure ↓	Day 7	Days 8-13	Day 14	Discharge Day 15	Follow-up Visit Day 21 (± 2)	End of Trial Visit Day 42 (± 3)
██████████							
Ambulatory BP monitoring		Start: pre: 0 ($\leq 15m$)	End: Day 8 preAM: 0 ($\leq 15m$)	Start: preAM: 0 ($\leq 15m$)	End: pd: 12h ($\pm 15m$)		
EndoPAT (j)			Day 13 preAM 0 (end $\geq 30m$)				
██████████					████████	█	█
Randomization							
Study drug administration (l)	AM	X	X	X			
	PM	X	X	X			
PK blood samples (m)	AM	pre: 0 ($\leq 5m$) pd: 1, 3, 6h ($\pm 5m$)	Day 8 pre: 0 ($\leq 5m$) pd: 1, 3, 6h ($\pm 5m$)	pre: 0 ($\leq 5m$) pd: 1,3,6h ($\pm 5m$)	pd: 12h ($\pm 15m$)	X	X
	PM	pre: 0 ($\leq 5m$)	Day 8 pre: 0 ($\leq 5m$)	pre: 0 ($\leq 5m$)			
Platelet function (n)			Day 8 preAM: 0 ($\leq 15m$)	preAM: 0 ($\leq 15m$)			
Confined to clinic		X	X	X			
Discharge from clinic					X		
Study completion							X

TABLE OF CONTENTS

STUDY IDENTIFICATION	2
SYNOPSIS.....	3
ELIGIBILITY CRITERIA.....	10
INCLUSION CRITERIA.....	10
EXCLUSION CRITERIA	12
SCHEDULE OF EVENTS	14
LIST OF ABBREVIATIONS AND DEFINITIONS OF TERMS.....	25
1. INTRODUCTION	28
1.1 BACKGROUND AND STUDY RATIONALE	28
1.2 IW-1973 BACKGROUND.....	29
2. STUDY OBJECTIVES.....	30
3. INVESTIGATIONAL PLAN.....	31
3.1 OVERALL STUDY DESIGN AND PLAN.....	31
3.2 DISCUSSION OF STUDY DESIGN INCLUDING THE CHOICE OF CONTROL GROUPS.....	33
3.3 STUDY DURATION	34
3.4 STUDY POPULATION SELECTION	34
3.4.1 Study Population.....	34
3.4.1.1 Type 2 Diabetes Requirement.....	34
3.4.1.2 Hypertension Requirement	34
3.4.2 Removal of Patients from Therapy or Assessment.....	35
3.4.3 Replacement Procedures	36
3.5 STUDY TREATMENT(S)	36
3.5.1 Study Drug.....	36
3.5.1.1 Investigational Product	36
3.5.1.2 Placebo	36
3.5.1.3 Packaging and Labeling.....	36
3.5.1.4 Storage and Accountability	36
3.5.2 Method of Assigning Patients to Treatment Groups.....	37
3.5.3 Selection of Dosage in the Study	37
3.5.4 Selection and Timing of Dose for Each Patient.....	37
3.5.5 Dosage.....	38
3.5.6 Blinding.....	38
3.5.7 Concomitant Medications	39
3.5.8 Restrictions	39
3.5.8.1 Prior Therapy and Prohibited Medications	39

3.5.8.2	Vitamins and Supplements	40

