2. STUDY OBJECTIVES

To compare the safety, tolerability, PK profile, and PD effects of 2 treatment regimens of IW-1973 Tablet (40 mg per day) administered orally for 2 weeks to patients with stable type 2 diabetes mellitus and hypertension.

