3.5.3 Selection of Dosage in the Study

This Phase 2a exploratory study will evaluate 40 mg IW-1973 administered daily for 2 weeks according to 2 different regimens: QD for both weeks or BID for the 1st week and QD the 2nd week. In the Phase 1b MAD study ([ICP-1973-102](#)), 40 mg IW-1973 was considered the maximum tolerated repeat dose, therefore, 40 mg was chosen for evaluation in this patient population.

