3.8.2.2 Day -1

- Weight
- If planned, EndoPAT assessment completed > 30 minutes before the time corresponding to AM dose on Day 13 and before all oral and any antihypertensive concomitant medications (Note: For each patient, the Day -1 and Day 13 assessments should occur at approximately the same time of day [± 15 minutes])
- Respiratory rate and oral temperature
- Collection of urine samples:
 - Urine albumin and creatinine (first void)
- Supine BP (average of 3 measurements) at the time corresponding to AM dose (≤ 15 minutes) on Day 1
- Supine-to-standing (orthostatic) pulse and BP
 - at the time corresponding to AM dose (≤ 30 minutes) on Day 1 and at 1 and 4 hours (± 5 minutes) after that time
 - at the time corresponding to PM dose (≤ 15 minutes) on Day 1 and at 1 and 4 hours (± 5 minutes) after that time (Note: Supine-only pulse and BP may be taken at the 4-hour post PM dose timepoint if, in the Investigator's clinical opinion, earlier orthostatic pulse and BPs indicate it is safe to eliminate the standing [orthostatic] pulse and BP measurement.)
- ABPM starts at the time corresponding to AM dose (≤ 15 minutes)
- AE evaluation
- Concomitant medication recording

3.8.2.3 Day 1

- Respiratory rate and oral temperature AM predose (≤ 30 minutes)
- Oral temperature at 1 and 4 hours (± 30 minutes) AM postdose
- 12-lead ECG predose (≤ 30 minutes) and at 4 hours (± 15 minutes) postdose
- Supine-to-standing (orthostatic) pulse and BP
 - AM predose (≤ 30 minutes) and at 1, 4 and 8 hours (± 5 minutes) postdose

- PM predose (\leq 15 minutes) and at 1 and 4 hours (\pm 5 minutes) postdose
(Note: Supine-only pulse and BP may be taken at the 4-hour post PM dose timepoint if, in the Investigator's clinical opinion, earlier postdose orthostatic pulse and BPs for the given dosing and for previous measurements at the 4-hour postdose timepoint indicate it is safe to eliminate the standing (orthostatic) pulse and BP measurement.)
- Collection of blood samples for:
 - PK
 - AM predose (\leq 15 minutes) and at 1, 3, and 6 hours (\pm 5 minutes) postdose
 - PM predose (\leq 5 minutes) and at 1 and 3 hours (\pm 5 minutes) postdose
 - Serum creatinine AM predose (\leq 15 minutes)
 - Hemoglobin A1c AM predose (\leq 15 minutes)
 - Fasting plasma glucose AM predose (\leq 15 minutes)
 - Fasting plasma insulin AM predose (\leq 15 minutes)
 - Platelet function assessments AM predose (\leq 15 minutes)
 - [REDACTED]
- Randomization

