3.8.2.5 Day 3-6

- Respiratory rate and oral temperature
- Supine pulse and BP AM predose (\leq 15 minutes)
- Study drug administration AM and PM, 12 hours (\pm 30 minutes) apart
- AE evaluation
- Concomitant medication recording

3.8.2.6 Day 7

- Respiratory rate and oral temperature
- Supine-to-standing (orthostatic) pulse and BP
 - AM predose (\leq 15 minutes) and at 1 and 4 (\pm 5 minutes) postdose
- ABPM starts AM predose (\leq 15 minutes)
- Collection of blood samples for PK:
 - AM predose (\leq 5 minutes) and at 1, 3, and 6 hours (\pm 5 minutes) postdose
 - PM predose (\leq 5 minutes)
- Study drug administration AM and PM, 12 hours (\pm 30 minutes) apart
- AE evaluation
- Concomitant medication recording

3.8.2.7 Day 8

- Respiratory rate and oral temperature
- ABPM ends AM predose (≤ 15 minutes)
- Supine-to-standing (orthostatic) pulse and BP
 - AM predose (≤ 15 minutes) and at 1 and 4 hours (± 5 minutes) postdose
 - PM predose (≤ 15 minutes)
- Collection of blood samples for:
 - PK
 - AM predose (≤ 5 minutes) and at 1, 3, and 6 hours (± 5 minutes) postdose
 - PM predose (≤ 5 minutes)
 - Hemoglobin A1c AM predose (≤ 15 minutes)
 - Fasting plasma glucose AM predose (≤ 15 minutes)
 - Fasting plasma insulin AM predose (≤ 15 minutes)
 - Platelet function assessments AM predose (≤ 15 minutes)
- Study drug administration AM and PM, 12 hours (± 30 minutes) apart
- AE evaluation
- Concomitant medication recording

3.8.2.8 Days 9 to 12

- Respiratory rate and oral temperature
- Supine pulse and BP AM predose (≤ 15 minutes)
- Study drug administration AM and PM, 12 hours (± 30 minutes) apart
- AE evaluation
- Concomitant medication recording

3.8.2.9 Day 13

- Weight
- If planned, EndoPAT assessment completed > 30 minutes before AM dose and before all oral and any antihypertensive concomitant medications; for each patient, assessments should be at time (± 15 minutes) of EndoPAT on Day -1
- Respiratory rate and oral temperature
- Supine-to-standing (orthostatic) pulse and BP
 - AM predose (≤ 15 minutes) and at 1 and 4 hours (± 5 minutes) postdose
 - PM predose (≤ 15 minutes)
- Study drug administration AM and PM, 12 hours (± 30 minutes) apart
- AE evaluation
- Concomitant medication recording

3.8.2.10 Day 14

- Respiratory rate and oral temperature
- Supine pulse and BP AM predose (≤ 15 minutes)
- ABPM starts AM predose (≤ 15 minutes)
- Collection of blood samples for:
 - PK
 - AM predose (≤ 5 minutes) and at 1, 3, and 6 hours (± 5 minutes) postdose

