3.8.2.11 Discharge (Day 15)

- Weight

- Respiratory rate and oral temperature
- ABPM ends 12 hours (\pm 15 minutes) postdose
- 12-lead ECG
- Supine BP (average of 3 measurements) and pulse at 12 hours (\pm 15 minutes) postdose
- Supine-to-standing (orthostatic) pulse and BP at 12 hours (\pm 15 minutes) postdose
- Physical examination
- Collection of blood at 12 hours (\pm 15 minutes) postdose:
 - PK
 - Clinical chemistry, hematology (CBC), coagulation
 - Hemoglobin A1c
 - Fasting plasma glucose
 - Fasting plasma insulin
 - [REDACTED]
- Collection of urine samples, first void
 - Urinalysis
 - Urine albumin and creatinine
- AE evaluation
- Concomitant medication recording
- Discharge from the clinic

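### No full safety panel, postdose creatinine or UACR is scheduled during the 14 dosing days, so the Week 1 BID versus QD laboratory contrast cannot be isolated

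*Protocol*

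**What the plan says.** Protocol Section 2 gives the objective as "To compare the safety, tolerability, PK profile, and PD effects of 2 treatment regimens of IW-1973 Tablet (40 mg per day", over two weeks. Section 3.5.3 defines the regimens as "QD for both weeks or BID for the 1st week and QD the 2nd week". Section 1.1 adds that the BID week is there to see whether tolerability improves.

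After dosing starts, the Schedule of Events row "Clinical chemistry, coagulation, hematology, urinalysis; (f" is marked at Day 15 and once in follow-up. The visit list in Section 3.8.3.2 places the follow-up panel at Day 42. The row "Urine albumin & creatinine (g" likewise has nothing between Day -1 and Day 15. The Discharge list (Section 3.8.2.11) includes "Clinical chemistry, hematology (CBC), coagulation", drawn 12 hours after the Day 14 evening dose.

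The Day 8 list (Section 3.8.2.7) has a fasting morning predose draw for PK, HbA1c, glucose and insulin, as well as "Platelet function assessments AM predose". It has no chemistry panel, hematology, coagulation, creatinine or urine sample. The SAP's Table 2 repeats this schedule.

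Protocol Sections 3.9.3.4.2 and 3.9.3.4.3 plan laboratory, UACR and eGFR changes by treatment group at every postdose timepoint. SAP 7.9.3 and 7.9.4 do the same for eGFR and UACR, but SAP 7.9.2 presents the quantitative laboratory parameters overall.

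**The concern.** The protocol otherwise treats Week 1 as a safety period of its own. Adverse events in the first 7 days are tabulated separately (protocol 3.9.3.4.1, SAP 7.9.1). Cuff pressure, ambulatory pressure and PK are all measured around Days 7 and 8, before the switch. The full panel, eGFR and UACR are not.

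Two things are at stake:

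- A laboratory or renal effect that differed between divided and single daily dosing in Week 1, and then faded once both arms were on the same regimen, would not appear in the data.
- No scheduled panel falls within any patient's dosing period. A laboratory abnormality can therefore feed the adverse-event-based stopping criteria (Section 3.6) during that patient's own dosing only if an unscheduled test picks it up. All patients take an ACE inhibitor or ARB (inclusion criterion 8a), and SAP 7.9.1 names bleeding as a possible class effect, so creatinine, hematology and coagulation matter here.

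**Working it through.** The documents give no power, effect size or SD for this point, so there is no planned figure to reproduce. The check is a count from the schedule, plus simple arithmetic.

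**1. Scheduled values, from the day-by-day lists in protocol Section 3.8**

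| Time | Full panel | Creatinine (eGFR) | UACR |
|---|---|---|---|
| Screening | yes | yes | yes |
| Day -2 | yes | yes | no |
| Day -1 | no | no | yes |
| Day 1, before first dose | no | yes | no |
| After first dose to end of Day 14 | no | no | no |
| Day 15 | yes | yes | yes |
| Day 21 | no | no | no |
| Day 42 | yes | yes | yes |

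Full panels after the first dose: 2. On treatment: 1 (Day 15). In Week 1 or before the Day 8 switch: 0. Footnote g of the schedule mentions a urine sample at the Follow-up Visit, while the visit lists place it at Day 42. Both visits are after the last dose, so the count is unaffected.

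**2. Overlap of the regimens** (protocol Table 3). The arms differ on 7 of 14 dosing days. From the Day 8 morning dose to the Day 15 morning sample is 7 × 24 = 168 hours of identical dosing.

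The documents state no half-life; SAP Section 8 says only that a 24-hour profile is too short to characterize it. As an assumption, the share of a Week 1 drug-level difference left after 168 hours is 2^(-168/t½):

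| Assumed t½ (h) | Share left |
|---|---|
| 12 | 0.006% |
| 24 | 0.8% |
| 48 | 8.8% |
| 72 | 20% |

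Laboratory effects may fade faster or slower than drug levels, so this is illustration only.

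**3. Time since active drug** (protocol Table 3 and Section 3.8.2)

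- Day 8 predose: the Day 7 evening dose is active in BID/QD and placebo in QD/QD, so the last active dose was about 12 hours earlier in BID/QD and about 24 hours earlier in QD/QD.
- Day 15: the Day 14 evening dose is placebo in both, so the last active dose was about 24 hours earlier in each arm.

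**4. Precision.** Allocation is 26 × 5/13 = 10, 26 × 5/13 = 10 and 26 × 3/13 = 6. The 95% CI half-width for a difference in means is t(0.975, df) × SD × √(1/n₁ + 1/n₂):

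- BID/QD versus QD/QD: 2.101 × √(1/10 + 1/10) = 0.94 SD (df 18).
- One active arm versus placebo: 2.145 × √(1/10 + 1/6) = 1.11 SD (df 14).

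These widths apply equally to Day 8 and Day 15 if all patients are measured.

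**The case against.** A reader might infer three stronger things that the documents do not support:

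- **That the laboratory data cannot compare the regimens at all.** The regimens are defined as two-week sequences, and Day 15 is a randomized comparison of exactly those, matched for time since active drug. It can show persistent or cumulative differences.
- **That Day 15 is the only panel after dosing starts.** Day 42 has a second one, off drug.
- **That no laboratory value exists for Week 1.** HbA1c, fasting glucose and insulin are drawn on Day 8 and are listed among the clinical laboratory tests in protocol Table 4. Platelet function is drawn then too.

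Beyond that, the stated purpose of the BID week is tolerability, which Week 1 adverse events, cuff pressures and ambulatory monitoring address. Both active arms receive 40 mg a day in Week 1, and nothing in the documents points to a laboratory effect that depends on dividing the dose. Patients are confined with daily adverse-event review, clinically significant laboratory abnormalities are reportable (protocol 3.7.3.9), and SAP 9.1 provides for unscheduled assessments. Changes that cause symptoms could therefore prompt a test. The study is exploratory and descriptive, so a Day 8 comparison would be as imprecise as the Day 15 one, with the added 12-hour versus 24-hour mismatch.

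All of this stands, and it limits the point to silent, transient changes and to the isolated Week 1 contrast. It does not close the gap: confinement and adverse-event review do not detect a silent creatinine, electrolyte, hematology or coagulation change.

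**Conclusion.** The point holds in limited form. Day 15 is the only on-treatment full panel, eGFR and UACR assessment, and it follows 7 days of identical dosing in the active arms. It supports a comparison of the two-week sequences with each other and with placebo; it does not isolate BID from QD in Week 1. A null difference at Day 15 should not be read as showing that the Week 1 regimens have the same laboratory effects. The number of scheduled values that could inform that question is 0, against up to 10, 10 and 6 with a Day 8 sample.

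This does not defeat the objective; it is a cheap improvement worth making. It assumes that no blacked-out item supplies a safety panel in Week 1 (the visible Day 8 list shows no redaction) and that the Investigator's Brochure, which is not available here, does not already justify the sparse schedule.

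A related inconsistency bears directly on the same comparison. SAP 6.1 presents safety data by treatment group unless otherwise indicated, and SAP 7.9.2 then indicates overall. Read literally, the descriptive laboratory summaries would not compare the regimens at any timepoint, contrary to protocol 3.9.3.4.2.

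**What to change.** - **Schedule:** add serum chemistry (with creatinine for eGFR), hematology and coagulation to the existing fasting Day 8 morning predose draw, and a first-void urine that morning for urinalysis and UACR.
- **SAP timepoints:** add Day 8 to the laboratory, eGFR and UACR summaries by treatment group.
- **SAP 7.9.2:** reconcile with protocol 3.9.3.4.2 so that laboratory values are summarized by treatment group.
- **Interpretation:** state in the SAP that Day 8 predose is about 12 hours after active drug in BID/QD and about 24 hours in QD/QD, and that the 10 versus 10 comparison is descriptive, with a half-width of about 0.94 SD. Read Day 15 as the comparison of the two-week sequences and of each with placebo.

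Cost: a few more mL of blood and laboratory fees for 26 patients, one schedule line and one SAP timepoint. Patients are confined and already being drawn, so no extra visit, needle stick or staff is needed. The change adds measurements only; it alters no dose or clinical rule.

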MedDRA	Medical Dictionary for Regulatory Activities
mg	milligram
mL	milliliter
mm Hg	millimeters of mercury
MPV	mean platelet volume
msec	millisecond
NO	nitric oxide

Abbreviation	Term
pd	postdose
PD	pharmacodynamic(s)
PDE	phosphodiesterase
PID	patient identification
PK	pharmacokinetic(s)
PT	preferred term
QTcF	QT interval corrected using Fridericia's formula
RBC	red blood cell
RDW	red blood cell distribution width
RHI	reactive hyperemia index
SAD	single ascending dose
SAE	serious adverse event
SAS®	Statistical Analysis System
Scr	serum creatinine
sGC	soluble guanylate cyclase
SGLT2	sodium-glucose co-transporter 2
SOC	system organ class
tau	dosing interval
t _{1/2}	apparent terminal phase half-life
T _{max}	time of maximum observed plasma concentration
UACR	urine albumin creatinine ratio
UGT	uridine diphosphate–glucuronosyl transferase
V _{z/F}	apparent volume of distribution (volume of distribution relative to bioavailability)
WBC	white blood cell

1. INTRODUCTION

1.1 BACKGROUND AND STUDY RATIONALE

The NO-sGC-cGMP (nitric oxide – soluble guanylate cyclase – cyclic guanosine 3',5'-monophosphate) pathway plays a critical role in the cardiovascular system. In the vascular endothelium, sGC is stimulated by NO to produce cGMP, which acts on downstream targets including cGMP-dependent protein kinases, phosphodiesterases, and ion channels. This leads to relaxation of the vascular smooth muscle and vasodilation. In addition, intracellular cGMP is involved in processes that affect vascular proliferation, fibrosis, and inflammation. Impaired NO-sGC-cGMP signaling, has been implicated in the pathogenesis of cardiovascular diseases such as systemic and pulmonary hypertension, coronary artery disease, congestive heart failure, peripheral vascular disease, atherosclerosis, and kidney disease. Agents that stimulate sGC to increase cGMP production (1,2) may be useful for treating and/or preventing a broad range of diseases that may ensue from dysfunction in the fundamental NO-sGC-cGMP pathway.(3,4)

This exploratory, proof-of-concept study will evaluate the safety, tolerability, PK, and PD of 2 dosing regimens of daily 40 mg IW-1973 administered orally for 2 weeks to patients with type 2 diabetes mellitus and hypertension. This study is designed to explore the tolerability profile of the MAD MTD, 40 mg IW-1973, in a patient population, and to explore whether tolerability can be improved with an initial week of BID dosing.

In addition to safety, tolerability, and PK, this study will evaluate the PD effects (hemodynamics and endothelial function) of daily 40 mg IW-1973 in patients with type 2 diabetes and hypertension, a population with likely dysfunction in the NO-cGMP-sGC pathway. Type 2 diabetes is a chronic metabolic disorder in which the body does not use insulin effectively, leading to hyperglycemia and glucose intolerance. The prevalence of diabetes in the United States (US) is 9.3%, or about 29.1 million people, and 95% of diagnosed cases are type 2.⁽⁵⁾ This multifactorial disease is associated with numerous comorbidities, including hypertension, obesity, hyperlipidemia, chronic kidney disease, and cardiovascular disease. Nearly all diabetic patients have at least 1 comorbidity and almost 90% have at least 2.⁽⁶⁾ Hypertension is the most common comorbid condition and may affect over 80% of patients with type 2 diabetes.⁽⁶⁾ Hypertension in diabetic patients increases the risk of cardiovascular disease and associated complications such as stroke, coronary artery disease, and peripheral vascular disease. In addition, hypertension in diabetic patients also increases the risk of microvascular diseases including retinopathy, nephropathy, and neuropathy.^(7,8) Many of the common comorbid disorders in diabetic patients are related to impairment in the NO-sGC-cGMP pathway; therefore, improving dysfunction in the NO-cGMP-sGC pathway could be useful in treating multiple disorders in these patients.

1.2 IW-1973 BACKGROUND

For a detailed description of the properties of IW-1973 and the results of the nonclinical and clinical studies conducted thus far, please refer to the most recent Investigator's Brochure.

2. STUDY OBJECTIVES

To compare the safety, tolerability, PK profile, and PD effects of 2 treatment regimens of IW-1973 Tablet (40 mg per day) administered orally for 2 weeks to patients with stable type 2 diabetes mellitus and hypertension.

3. INVESTIGATIONAL PLAN

3.1 OVERALL STUDY DESIGN AND PLAN

[figure not shown]
This is a randomized, double-blind, placebo-controlled study consisting of 3 distinct periods (see [Figure 1](#)). The study will enroll 26 patients (at least 11 male and 11 female) with stable type 2 diabetes and hypertension (see [Eligibility Criteria](#)). Additional patients may be checked into the Study Center on Day -2 as backups. If the backup patients are not needed, they will be discharged from the Study Center before Randomization. Patients withdrawing from the study after Randomization will not be replaced. Patients will be randomized in a 5:5:3 ratio to 1 of 2 IW-1973 treatment regimens or placebo (all regimens will be masked) as outlined in [Table 2](#).

Table 2. Treatment Arm Dosing Regimens

Treatment Arm	Dose time	Days 1 to 7	Days 8 to 14
QD/QD	AM	40 mg IW-1973	40 mg IW-1973
	PM	Placebo	Placebo
BID/QD	AM	20 mg IW-1973	40 mg IW-1973
	PM	20 mg IW-1973	Placebo
PBO/PBO	AM	Placebo	Placebo
	PM	Placebo	Placebo

Refer to Section [3.5.5](#) for details on the number of IW-1973 and/or placebo tablets that will make up each dose.

Figure 1. Study Schematic

The 26 patients may be enrolled separately. Each patient will progress through 3 study periods.

Screening Period: The Screening Period will begin with the signature of the informed consent form (ICF) at the Screening Visit (which can occur from Day -28 to Day -3) and will last 1 to 26 days. At the Screening Visit, patients will undergo preliminary screening procedures to determine their eligibility for the study. The end of the Screening Period will coincide with the beginning of the Clinic Period at Check-in.

Clinic Period: The Clinic Period will begin at Check-in on Day -2 (2 days before dosing) and will end at the time of Discharge on Day 15. During the 17-day Clinic Period, patients will be confined to the Study Center and will receive a standard diet for diabetics. Patients who meet eligibility criteria based on Screening Visit assessments will be admitted to the Study Center on Day -2 for baseline procedures. On the morning of Day 1 (there is no Day 0), eligible patients will be randomized 5:5:3 to 1 of 3 masked treatment regimens: QD/QD, BID/QD, or PBO/PBO. On Days 1 to 14, patients will receive a morning (AM) dose and an evening (PM) dose. See Section 3.5.4 for details on dosing.

Safety, PK, and PD assessments, including blood collections, will be performed at specified times throughout the Clinic Period (see [Schedule of Events](#)). On Day 15, after assessments have been completed, patients will be discharged from the Study Center at the Investigator's discretion.

Follow-up Period: The Follow-up Period will begin immediately after Discharge from the Study Center on Day 15 and will last for 27 (\pm 3) days. On Day 21 (\pm 2 day), 7 (\pm 2) days after the last dose of study drug, patients will return to the Study Center for the Follow up Visit (see [Schedule of Events](#)). On Day 42 (\pm 3 days), 28 days after the last dose of study drug, patients will return to the Study Center for the End of Trial Visit.

